#### o Hepatic function:

- Total Bilirubin: ≤1.5xULN OR Direct bilirubin ≤ULN for subjects with total bilirubin levels >1.5xULN
- AST (SGOT) and ALT (SGPT): ≤2.5xULN OR ≤5xULN for subjects with liver metastases

#### o Coagulation:

- International Normalised Ratio (INR) or Prothrombin Time (PT): ≤1.5xULN unless subject is receiving anticoagulant therapy as long as PT or PTT is within therapeutic range of intended use of anticoagulants
- Activated Partial Thromboplastin Time (aPTT): ≤1.5xULN unless subject is receiving anticoagulant therapy as long as PT or PTT is within therapeutic range of intended use of anticoagulants

.

<sup>3 Coagulation test should be within normal limits unless the patients are being treated with anticoagulant in which case the values allowed for injection and biopsy as well as the timing to stop anticoagulants before injection and biopsy will be determined at each site according to institutional guidelines.

agalin A subsidiary of Bio	OLINE AX	PRIVILEGED & CONFIDENTIAL
Investigational Product: AGI-134	A Phase I/IIa, multicentre, two-parts, open label study designed to evaluate the safety and tolerability of escalating	Protocol No. AGI-134.FIM.101
Phase: I/IIa	doses of AGI-134 in unresectable/metastatic solid tumours.	Version 6.1 31 May 2021

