  - O Part 1: The total size of the tumour(s) should allow injection of the total volume required at each escalation cohort. The volume can be injected into one lesion or divided into more than one lesion, but the total volume should be given according to the total dose at each escalation part. When volume is divided between several tumours, at least 1 mL should be injected into each tumour.
  - o Part 2: Tumour dimensions should allow injection of a minimum of 1 mL.
- 8. Has  $\geq$  2 lesions
  - Has ≥1 injectable lesion which is amenable to injection and biopsy and is evaluable according to RECIST v1.1.
  - Has another lesion which is amenable for biopsy and is evaluable according to RECIST v1.1. Superficial large lesions of more than 25 cm can be considered as two lesions upon discussion with and approval by the Sponsor.
- 9. Evaluable Disease according to RECIST v1.1
- 10. Has an Eastern Cooperative Oncology Group (ECOG) Performance Status score of 0 or 1.
- 11. Has a life expectancy >3 months

		PRIVILEGED & CONFIDENTIAL
Investigational Product: AGI-134		Protocol No. AGI-134.FIM.101
Phase: I/IIa		Version 6.1 31 May 2021

- 12. Adequate organ function at Screening as defined below. All laboratory assessments should be performed within 10 days prior to treatment initiation.
  - o Haematology:
    - White blood cell (WBC)  $\geq 2,500/\text{mm}^3$
    - Absolute neutrophil count ≥ 1500 /mm^3
    - Platelet count  $\geq 100,000/\text{mm}^3$
    - Haemoglobin ≥9 g/dL or ≥5.6 mmol/L
    - Haematocrit >30%
  - Renal function:
    - Creatinine ≤1.5x Upper limit of normal (ULN) OR measured or calculated creatinine clearance (glomerular filtration rate [GFR]) can also be used in place of creatinine or CrCl) > 50 mL/min for subject with creatinine levels > 1.5x institutional ULN
  - o Hepatic function:
    - Total Bilirubin: ≤1.5xULN OR Direct bilirubin ≤ULN for subjects with total bilirubin levels >1.5xULN
    - AST (SGOT) and ALT (SGPT): ≤2.5xULN OR ≤5xULN for subjects with liver metastases
  - Coagulation
    - International Normalised Ratio (INR) or Prothrombin Time (PT): ≤1.5xULN unless subject is receiving anticoagulant therapy as long as PT or PTT is within therapeutic range of intended use of anticoagulants
    - Activated Partial Thromboplastin Time (aPTT): ≤1.5xULN unless subject is receiving anticoagulant therapy as long as PT or PTT is within therapeutic range of intended use of anticoagulants

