## **Screening Procedures:**

- ICF signature
- Inclusion/Exclusion Criteria review
- Collection of demographic data
- Collection of medical history
- Collection of disease history (including genetic information, dMMR/MSI/TMB)
- Collection of disease treatment history
- Review of prior (up to one year) and concomitant medications
- AE recording
- 12-lead electrocardiogram (ECG) local reading
- Full physical examination
- Vital signs (blood pressures, pulse rate, O2 saturation, oral temperature in °C, respiratory rate)
- Weight
- Height
- Urinalysis
- ECOG performance status
- Blood will be drawn for:
  - o Serum pregnancy test
  - o FSH for women who reported menopause for less than two years
  - o Disease markers according to each subject's disease
  - HPV status for relevant indications (HPV status assessment should be performed at local lab in case no available status from the time of diagnosis)
  - PT/INR and Activated Partial Thromboplastin Time (aPTT)
  - CBC with differential
  - Biochemistry panel
  - o T3, free T4 and thyroid stimulating hormone (TSH)
  - o HIV, HBV and HCV serology

<sup>10 For subjects on anticoagulant treatment, coagulation test should be performed within 24 before the injection and biopsy at Baseline. Anticoagulants should be stopped for injection and biopsy according to institutional guidelines.

<sup>11 The coagulation test should be within normal limits unless the subjects are being treated with an anticoagulant in which case the values allowed for injection and biopsy as well as the timing to stop anticoagulants before injection and biopsy will be determined at each site according to institutional guidelines.

agalin A subsidiary of BIO		PRIVILEGED & CONFIDENTIAL
Investigational Product: AGI-134		Protocol No. AGI-134.FIM.101
Phase: I/IIa	doses of AGI-134 in unresectable/metastatic solid tumours.	Version 6.1 31 May 2021

- o Blood for anti-Gal IgE
- Tumour imaging. A standard of care imaging performed prior to ICF signature, which were done according to the imaging manual guidelines (Please refer to the *Imaging Manual* for more details) and are within the screening window will be allowed for eligibility.
- RECIST v.1.1 assessment

Subjects may be rescreened after consultation with the Sponsor.

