#### 5.12.2 Planned Biopsy Analysis

Biopsies will be performed at baseline and Cycle 3 from injected lesion as well as from uninjected lesion.

Additional biopsy from superficial injected lesion will be performed on Cycle 1 Day 3 (48-72 hours) post AGI-134 administration. This biopsy is mandatory for superficial injected lesions

VS		PRIVILEGED & CONFIDENTIAL
Investigational Product: AGI-134		Protocol No. AGI-134.FIM.101
Phase: I/IIa	doses of AGI-134 in unresectable/metastatic solid tumours.	Version 6.1 31 May 2021

and is also requested for deep lesions, unless not considered in the best interest for the patient by the PI.

Procedures, collection, storage and shipping instruction will be provided in the *Administration* of AGI-134 and Tumour Biopsy Procedures in Study AGI-134.FIM.101 document.

The reason for a missing biopsy assessment should be documented within the eCRF. All efforts should be done in order to conduct all the biopsy assessments as required in the protocol.

Two core biopsies are required to be taken at each timepoint and from each lesion. All biopsies will be processed as Formalin-Fixed Paraffine-Embedded (FFPE) blocks.

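### For subjects not on anticoagulants, inclusion criterion 12 accepts PT/INR and aPTT up to 1.5xULN, while its own footnote asks for values within normal limits

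*Combined protocol and SAP*

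**What the plan says.** **The criterion.** In the Synopsis, criterion 12 lists under Coagulation "International Normalised Ratio (INR) or Prothrombin Time (PT): ≤1.5xULN unless subject is receiving anticoagulant therapy" and "Activated Partial Thromboplastin Time (aPTT): ≤1.5xULN unless subject is receiving anticoagulant therapy". Both carry the exception "as long as PT or PTT is within therapeutic range of intended use of anticoagulants". Section 4.1 repeats the same limits, and its Coagulation heading again carries marker 3.

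**The footnotes.** Footnote 3 in the Synopsis reads "Coagulation test should be within normal limits unless the patients are being treated with anticoagulant". For treated patients it adds that the values acceptable for injection and biopsy, and the timing of stopping the anticoagulant, "will be determined at each site according to institutional guidelines". In Section 5.1, footnote 11 is attached to the screening PT/INR and aPTT and states "The coagulation test should be within normal limits unless the subjects are being treated with an anticoagulant". The rescreening list in the same section carries marker 11 on the same test.

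**Related rules.**
- PT/INR and aPTT are repeated at Baseline (Section 5.2) and before dosing in Cycles 2, 3 and 4 (Section 5.3.4), with results to be in hand before the injection. Note 10 to Table 6 (Part 1) extends this to biopsies.
- The sponsor reviews and approves eligibility before a subject enters (Synopsis, Screening Visit; Section 5.1).
- Section 9.8 bars prospective waivers of the entry criteria.
- On biopsies, Section 5.12.2 says "Biopsies will be performed at baseline and Cycle 3 from injected lesion as well as from uninjected lesion". It adds one on Cycle 1 Day 3, of which it says "This biopsy is mandatory for superficial injected lesions".

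**The concern.** An eligibility criterion should give one answer for one laboratory value. Here the body of the criterion gives a numeric ceiling above the upper limit of normal, and a footnote on its heading gives a stricter rule. Two people reading the same page can reach opposite decisions about the same subject, each with text to support them.

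The subjects concerned will have needles placed in tumours for injection and for biopsy, and safety and tolerability is the primary endpoint (Section 2.2.1). The clotting limit at entry is therefore part of the definition of the population in which safety is described. Because waivers are barred, discretion cannot resolve the matter for a given subject, and the written rule has to do so.

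**Working it through.** The plan gives no figure to reproduce. The check is a comparison of the two rules for a subject not on an anticoagulant.

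**Inputs.** Criterion 12 (Synopsis and Section 4.1): INR or PT at most 1.5xULN, and aPTT at most 1.5xULN. Footnotes 3 and 11: within normal limits, so an upper bound of 1.0xULN.

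| PT/INR or aPTT (other test normal) | Criterion 12 | Footnotes 3 and 11 |
|---|---|---|
| In the normal range, up to 1.0xULN | accepts | accept |
| Above 1.0 and up to 1.5xULN | accepts | do not accept |
| Above 1.5xULN | does not accept | do not accept |

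The rules disagree over the whole of the middle row, a band of 1.5 − 1.0 = 0.5xULN. For example, a value of 1.3xULN passes the criterion (1.3 ≤ 1.5) and fails the footnotes (1.3 > 1.0).

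**Does any text settle which rule applies?**
1. Placement. Footnote 3 is attached to an inclusion criterion and footnote 11 to the screening and rescreening tests. Neither is attached to a dosing or biopsy instruction.
2. Wording. In both footnotes the mention of injection and biopsy sits in the clause about anticoagulated patients. The clause on normal limits has no such restriction.
3. Pre-injection checks. Sections 5.2 and 5.3.4 and note 10 to Table 6 ask for results in advance but name no threshold, so they supply no separate procedure-day limit to which the footnotes could be assigned.
4. Precedence. No section says that the criterion overrides its footnote, or the reverse.

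**If the footnotes are taken as a procedure-day rule anyway.** A subject enrolled at 1.3xULN whose Baseline repeat is also 1.3xULN would be eligible, yet would not meet the footnote when the first injection is due. The plan does not say what follows.

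**Subjects exposed to the ambiguity.** Planned enrolment is up to 24 in Part 1 and about 35 in Part 2, so up to about 24 + 35 = 59 treated subjects. The documents do not say what share would be off anticoagulants with a value in the band, so no count can be derived.

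**The case against.** The best defence is that the footnotes describe readiness for a procedure and not entry. They are phrased as a recommendation where the criterion gives a number, they mention injection and biopsy, and the plan does repeat coagulation tests before each dosing. This is a plausible account of what was intended. It does not remove the conflict, because the footnotes are attached to entry and screening items and nothing written limits them to the procedure day.

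A second defence is sponsor approval of every entry. This stands in part: central review can make decisions more uniform. A reader might infer that sites will admit different risk populations, but with that control in place the documents support only that they could. The approver still has no text that settles the question.

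Three further inferences are tempting and not supported:

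- **A second contradiction for anticoagulated subjects.** The criterion asks for the therapeutic range, and the footnote leaves values to the site. But the footnote speaks there of values for injection and biopsy and of when to stop the drug. Footnote 10 in Section 5.1 likewise ties testing in these subjects to the Baseline injection and biopsy. A subject can meet the therapeutic-range rule at entry and then be managed by local rules before the procedure, so the two statements are compatible.
- **Damage to the Per-Protocol set.** That set, defined under Analysis Sets in Section 8, removes only major violations. Nothing available says a mildly raised value would count as major, and no analysis shown is assigned to that set. The detailed SAP to which Section 8.2 defers is not among the documents.
- **The biopsy schedule as a measure of size.** A Part 2 subject may have 2 + 1 + 2 = 5 lesion biopsies (Baseline, Cycle 1 Day 3, Cycle 3) and four dosing sessions. This is exposure common to Part 2 subjects generally. It explains why clotting limits matter, but does not measure how many subjects the conflict touches.

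**Conclusion.** The inconsistency is real and the text is wrong as written. For subjects not on anticoagulants, the same criterion and its footnote give opposite answers for every PT/INR or aPTT value above 1.0 and up to 1.5xULN. This rests only on reading normal limits as ending at the ULN and on the absence of any text that ranks the rules or confines the footnotes to procedure days.

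The reach is limited. The number of affected subjects is unknown, no bleeding rate can be inferred, and the Safety Population, being everyone dosed, is the same under either rule once a subject has been treated. What the conflict can change is who is enrolled. It is an internal inconsistency in wording, minor in scale, but it bears on patient safety and is worth removing because the correction is nearly free. Which limit is appropriate is a clinical decision and is not judged here.

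**What to change.** Reconcile criterion 12 in the Synopsis and Section 4.1 with footnote 3, and with footnote 11 where it is attached to the screening and rescreening tests in Section 5.1, so that one coagulation limit governs entry for subjects not on anticoagulants. State separately whether any limit applies on the day of injection or biopsy. If one does, place it with the pre-injection checks in Sections 5.2 and 5.3.4 and in the notes to Tables 6 and 7. The sponsor decides the values.

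The cost is an amendment to a few lines of text. It needs no additional tests, visits or subjects, because PT/INR and aPTT are already measured at each of these points.

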# 13. Women of childbearing potential and all men must agree to use 2 Inclusion methods of an adequate contraception: One barrier method (e.g. Criteria diaphragm, or condom or sponge, each of which are to be combined with a spermicide) and one hormonal method (e.g. oral, transdermal patch, implanted contraceptives or intrauterine device) prior to study entry and for the duration of study participation through 120 days after the last dose of study treatment. Subjects that are highly unlikely to conceive (e.g. surgically sterile, postmenopausal, or not heterosexually active) are exempt. Confirmation that female subjects are not pregnant must be established by a negative serum β-human chorionic gonadotropin (βhCG) pregnancy test result obtained during Screening. Pregnancy testing is not required for postmenopausal or surgically sterilised women. Non-childbearing potential is defined as (by other than medical reasons): • ≥45 years of age and has not had menses for over 2 years. <45 years of age and amenorrhoeic for > 2 years without a hysterectomy and oophorectomy and a Follicle Stimulating Hormone (FSH) value in the postmenopausal range upon pretrial (screening) evaluation. For women, post hysterectomy, bilateral oophorectomy, bilateral salpingectomy or bilateral tubal ligation and vasectomy for men at least 6 weeks prior to screening. Documented hysterectomy or oophorectomy must be confirmed with medical records of the actual procedure or confirmed by ultrasound. Tubal ligation must be confirmed with medical records of the actual procedure. 14. Subject is able and willing to comply with the requirements of the protocol. 15. Subject is able to voluntarily provide written informed consent. Exclusion Subject must be excluded from participating in the study if he/she: criteria 1. Has a disease that is suitable for therapy administered with curative intent. 2. Has any active, acute, or chronic infection(s) that are uncontrolled and/or requiring treatment, such as antibiotics.

agalin A subsidiary of Bio	nnune DLINERX	PRIVILEGED & CONFIDENTIAL
Investigational Product: AGI-134		Protocol No. AGI-134.FIM.101
Phase: I/IIa	doses of AGI-134 in unresectable/metastatic solid tumours.	Version 6.1 31 May 2021

# Exclusion criteria

- 3. An active autoimmune disease that has required systemic treatment in the 2 years preceding the study (i.e., with the use of disease-modifying agents, corticosteroids or immunosuppressive drugs). Note: Replacement therapy (e.g., thyroxine, insulin, or physiologic corticosteroid replacement therapy for adrenal or pituitary insufficiency, etc.) is not considered a form of systemic treatment and is allowed.
- 4. History of or plan for splenectomy or splenic irradiation.
- 5. History of organ transplant or currently taking active immunosuppressive therapy such as cyclosporine, tacrolimus, etc.
- 6. Has a known history of Human Immunodeficiency Virus (HIV) (HIV 1/2 antibodies).
- 7. Has known active Hepatitis B (e.g., Hepatitis B Surface Antigen [HBsAg] reactive) or Hepatitis C (e.g., Hepatitis C Virus [HCV] RNA [qualitative] is detected).
- 8. Has known Chronic Hepatitis B or C.
- 9. History or evidence of cancer associated with immunodeficiency states (e.g. hereditary immune deficiency, organ transplant, or leukaemia).
- 10. Has a diagnosis of immunodeficiency or is receiving systemic steroid therapy or any other form of immunosuppressive therapy within 7 days prior to the first dose of study treatment.
- 11. Is expected to require any other form of antineoplastic therapy while on study.
- 12. Has positive IgE anti-Gal
- Subject has a known allergy to alpha-Gal, such as red meat allergy, exposure to lone star tick (Amblyomma americanum), Ixodes ricinus/ holocyclus.
- 14. Has known allergy or hypersensitivity to any of the test compounds, materials, or contraindication to test product.
- 15. History or evidence of central nervous system metastases and/or carcinomatous meningitis (unless stable without treatment for at least 6 weeks and not requiring steroids).
- 16. Has received other experimental therapies or used an investigational device within 28 days of the first dose of treatment.

<sup>4 Note: Subjects with previously treated brain metastases may participate provided they are stable (without evidence of progression by imaging using the identical imaging modality for each assessment, either MRI or CT scan, for at least four weeks prior to the first dose of study treatment and any neurologic symptoms have returned to baseline), have no evidence of new or enlarging brain metastases, and are not using steroids for at least 7 days prior to study treatment. This exception does not include carcinomatous meningitis which is excluded regardless of clinical stability

agalin A subsidiary of Bio	nnune DLINERX	PRIVILEGED & CONFIDENTIAL
Investigational Product: AGI-134		Protocol No. AGI-134.FIM.101
Phase: I/IIa	doses of AGI-134 in unresectable/metastatic solid tumours.	Version 6.1 31 May 2021

# Exclusion criteria

- 17. Has had prior chemotherapy, targeted small molecule therapy, or radiation therapy within 14 days before first AGI-134 administration or has not recovered from treatment related AE >Grade 1.
- 18. Has had a prior anti-cancer monoclonal antibody (mAb) treatment within 28 days before first AGI-134 administration or who has not recovered from AE > Grade 1.
- 19. Is pregnant or breastfeeding or expecting to conceive or father children within the projected duration of the study, starting with the Screening visit through 120 days after the last dose of study treatment. Women with a positive pregnancy test within 72 hours from Baseline.
- 20. Has unstable angina, new onset angina within the last 3 months, myocardial infarction within the last 6 months, uncontrolled atrial fibrillation, or current congestive heart failure with New York Heart Association Class III or higher.
- 21. Has a known current additional malignancy that is progressing or requires active treatment. Exceptions are non-melanoma skin lesions, adequately treated basal cell or squamous cell carcinoma that has undergone potentially curative therapy or carcinoma in situ of the cervix.
- 22.  $O_2$  saturation < 92% (on room air).
- 23. Has an underlying medical condition that would preclude study participation or other psychological, social, or physical examination (PE) finding or a laboratory abnormality that the PI considers would make the subject a poor study candidate or could interfere with protocol compliance or the interpretation of study results.
- 24. Has known psychiatric or substance abuse disorders that would interfere with cooperation with the requirements of the study.

<sup>5 Subjects with ≤ Grade 2 neuropathy or ≤ Grade 2 alopecia are an exception to this criterion and may qualify for the study. If subject underwent major surgery, they must have recovered adequately from the toxicity and/or complications from the intervention prior to starting therapy.

agalin A subsidiary of Bit	OLINERX	PRIVILEGED & CONFIDENTIAL
Investigational Product: AGI-134	A Phase I/IIa, multicentre, two-parts, open label study designed to evaluate the safety and tolerability of escalating	Protocol No. AGI-134.FIM.101
Phase: I/IIa	doses of AGI-134 in unresectable/metastatic solid tumours.	Version 6.1 31 May 2021

# Investigational Product Route and Dosage Form

The investigational product in this study is AGI-134. The drug is provided as a 25 mg/mL sterile dispersion in phosphate buffered saline (PBS).

In the dose escalation phase, AGI-134 will be administered by intralesional injection at escalating total doses of 25 mg (1 mL), 50 mg (2 mL), 100 mg (4 mL) and up to 200 mg (8 mL) in 3-week cycles until progression, toxicity or 4 cycles completion, whichever comes first. The total volume of the AGI-134 injection may be divided to more than one lesion while maintaining a minimum of 1 mL per injection site. In Part 2 of the study, the treatment schedule will be the same, and the dose of AGI-134 used will be according to the lesion dimensions and up to the RP2D.

